11.2 Analysis Plan

The primary analysis within each cohort will done on patients who receive at least one dose of nelfinavir, and anti-PD-1/PD-L1 therapy and at least one fraction of radiation. The safety analysis population will include all patients who receive at least one dose of any of the study drugs.

Binary endpoints (response, toxicity) will be summarized as proportions with associated 90% Clopper-Pearson confidence intervals. With 20 patients per cohort, binary proportions can be estimated to within 18% with 90% confidence. Any toxicity with true prevalence of at least 10% is likely to be observed (with 88% probability).

The distribution of time-to-event endpoints will be estimated using the method of Kaplan-Meier to derive estimates for median times and percentages at landmark times (e.g. 6 months). Confidence intervals for median times will be estimated using the Brookmeyer-Crowley method and for landmark times will be calculated using Greenwood's formula and based on a log-log transformation applied on the survival function.

A logistic regression model will be used to assess the association between response and factors such as smoking within each cohort. These associations will be summarized by odds ratios and associated confidence intervals and p-values. A Cox regression model will be used to assess the association between time-to-event outcomes (PFS,OS) and factors within each cohort. Similarly, these associations will be summarized by hazard ratios and associated confidence intervals and p-values.

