3.0 STUDY AGENT INFORMATION

3.1 Immunotherapy Reference Therapy

PD1/PDL1 immune checkpoint inhibitor will delivered intravenously per standard of care.

Keytruda® (Pembrolizumab) FDA Approved Dosage and Administration

Metastatic Melanoma	200 mg intravenously over 30 minutes Every 3 weeks
Metastatic Non-Small Cell Lung Cancer	200 mg intravenously over 30 minutes Every 3 weeks

[figure not shown]
Opdivo® (Nivolumab) FDA Approved Dosage and Administration

Metastatic Melanoma	240 mg every 2 weeks or 480 mg every 4 weeks, intravenously over 30 minutes
Metastatic Non-Small Cell Lung Cancer	240 mg every 2 weeks or 480 mg every 4 weeks, intravenously over 30 minutes
Advanced Renal Cell Carcinoma	240 mg every 2 weeks or 480 mg every 4 weeks, intravenously over 30 minutes

Tecentriq® (Atezolizumab) FDA Approved Dosage and Administration

Metastatic Non-Small Cell Lung Cancer	1,200 mg intravenously over 60 minutes Every 3 weeks
---------------------------------------	---

Selection Pathway: In order of site preference

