4.3 Criteria for Removal/Withdrawal from Treatment

- 4.3.1 Subjects may be removed from this study at any time at their discretion. Subjects may also be removed from this protocol if they develop any untoward side effects from the study medication. In addition there are stopping rules in place for lack of efficacy and excessive toxicity as detailed in the statistical section.
- 4.3.2 Disease progression will be clinically determined by the principal investigator. Patients who show disease progression will be taken off of the study.
- 4.3.3. Extraordinary Medical Circumstances. If at any time the constraints of this protocol are detrimental to the subject's health, the subject will be removed from protocol therapy. In this event, the reasons for withdrawal will be documented.

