6.2 Hypofractionated Radiotherapy

Hypofractionated radiotherapy typically involves fewer fractions over fewer days but each fraction involves a higher dose, compared with conventional radiation techniques. The goal of HIGRT/SBRT in this setting is to deliver appropriate tumor directed palliation while minimizing exposure of surrounding normal tissues. The dose used to treat a given tumor will be based on the location of the lesion, as the organs at risk surrounding the lesion are likely to dictate the risk of normal tissue toxicity. The study will exclude irradiation of liver metastases as an added precaution.

Patients will undergo a 3 fraction HIGRT/SBRT regimen, treatment commencing between 1st and before 3rd cycle of PD1/PDL1 immune checkpoint inhibitor. Dose and fractionation will be determined per standard clinical practice and will be dependent on the location of the treated site and adjacent organs at risk.

Either 3D-conformal radiotherapy or intensity-modulated radiotherapy (including volumetric arc radiotherapy [VMAT]) is acceptable planning techniques. Planning techniques may differ for each lesion to be treated provided that tumor motion is properly accounted for with each technique when the target is near the thorax region (i.e. lung or liver). Daily image guidance is required for this study.

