6.6 Duration of Therapy

Reference PD1/PDL1 inhibitor therapy ends at the time of progression (as defined by Response Evaluation Criteria in Solid Tumors (RECIST) version 1.1 (irRECIST v1.1) by physical examination and radiographic assessment, primarily CT scan, immune response criteria and/or loss of clinical benefit as assessed by the investigator). The study period is defined from the time of consent through the follow-up period or end of service. The last follow-up appointment occurs 6-months after the last dose of nelfinavir. Patients will be seen prior to end of service as per standard of care. Additional endpoints will include overall survival and safety.

6.7 Rationale for Allowing Patients to Continue PD1/PDL1 immune checkpoint inhibitor Treatment until Loss of Clinical Benefit

Conventional response criteria may not adequately assess the activity of immunotherapeutic agents because progressive disease (by initial radiographic evaluation) does not necessarily reflect therapeutic failure. Because of the potential for pseudo progression/tumor immune infiltration, this study will allow patients to remain on PD1/PDL1 immune checkpoint inhibitor after apparent radiographic progression, provided the benefit-risk ratio is judged to be favorable. Patients should be discontinued for unacceptable

toxicity or symptomatic deterioration attributed to disease progression as determined by the investigator after an integrated assessment of radiographic data, biopsy results (if available), and clinical status. Patients who show evidence of clinical benefit will be permitted to continue PD1/PDL1 immune checkpoint inhibitor after RECIST v1.1 criteria for progressive disease are met if they meet all of the following criteria:

- Evidence of clinical benefit as assessed by the investigator
- Absence of symptoms and signs (including worsening of laboratory values, e.g., new or worsening hypercalcemia) indicating unequivocal progression of disease
- No decline in ECOG performance status that can be attributed to disease progression
- Absence of tumor progression at critical anatomical sites (e.g., leptomeningeal disease) that cannot be managed by protocol-allowed medical interventions
- Patients for whom approved therapies exist must provide written consent to acknowledge deferring these treatment options in favor of continuing study treatment at the time of initial progression

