6.8 Off Treatment Criteria

Patients will be removed from protocol therapy when any of the criteria listed in Section 6.3.8 applies. The source document will give the reason for ending protocol therapy and the date the patient was removed from treatment. All patients who discontinue treatment should comply with protocol specific follow-up procedures as outlined in Appendix 14.4. There are two exceptions to this requirement:

- Patient starts a new anti-cancer therapy and/or receives additional radiation treatment prior to follow-up procedures
- Patient withdraws consent for all study procedures or loses the ability to consent freely.

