6.9 Duration of Follow-Up

Patients will be followed after completion or removal from protocol treatment at two protocol-mandated time points. The first follow-up will occur 1 month after last dose of Nelfinavir (+/- 2 weeks), while the second follow-up will occur 6 months from date of enrollment (+/- 2 weeks). All patients who discontinue treatment should comply with the procedures below unless they meet the exceptions in Section 6.8:

- Physical Exam; ECOG
- Adverse Events Monitoring
- Concomitant Medication Monitoring
- Response Assessment by irRECIST 1.1
- Research Blood Collection
- Optional tumor biopsy

Survival follow-up will continue for 2 years from enrollment through office visits (scheduled at clinically indicated intervals, will vary by patient) and by review of medical record. Subjects may be contacted by phone call every 6 months to determine vital status.

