6.11 Patient Replacement

A patient who is enrolled but did not receive any protocol therapy (one dose of PD1/PDL1 immune checkpoint inhibitor) is considered non-evaluable, and will be replaced.

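### The primary response analysis (11.2) leaves out patients who start the inhibitor but are never irradiated, and the replacement rule (6.11) does not cover them, so the response rate may be overstated and the operating characteristics are unclear

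*Combined protocol and SAP*

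**What the plan says.** - **Analysis set (11.2).** The primary analysis in each cohort is done on "patients who receive at least one dose of nelfinavir, and anti-PD-1/PD-L1 therapy and at least one fraction of radiation". The safety set is wider: one dose of any study drug is enough.
- **Replacement (6.11).** An enrolled patient who "did not receive any protocol therapy (one dose of PD1/PDL1 immune checkpoint inhibitor) is considered non-evaluable, and will be replaced". Radiation plays no part in this rule.
- **Timing (6.2, 3.1, 9.2).** Radiation is given with "treatment commencing between 1st and before 3rd cycle of PD1/PDL1 immune checkpoint inhibitor". Nivolumab may be given at "240 mg every 2 weeks or 480 mg every 4 weeks, intravenously over 30 minutes"; pembrolizumab and atezolizumab are 3-weekly. The first response scan is at weeks 12-14 after the inhibitor starts (9.2).
- **Ways out before radiation.** Section 4.3.2: "Patients who show disease progression will be taken off of the study". Section 6.8 removes a patient from protocol therapy when any 6.3.8 toxicity criterion is met.
- **Missing responses (2.3.1).** A patient with no known response counts as a non-responder.
- **Assessment after stopping (6.9).** "All patients who discontinue treatment should comply with the procedures below unless they meet the exceptions in Section 6.8"; irRECIST assessment is among those procedures. One exception is "Patient starts a new anti-cancer therapy and/or receives additional radiation treatment prior to follow-up procedures".
- **Size (11.1, synopsis, 11.4).** Section 11.1 plans 20 patients in each of six cohorts, 120 in all, described as evaluable for response. The synopsis gives 120 as a maximum and 11.4 plans to enrol 120.

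**The concern.** Sections 6.11 and 11.2 use different triggers. Losses during the nelfinavir run-in are replaced. Losses between the first inhibitor dose and the first radiation fraction are neither replaced nor counted in the primary response analysis. They appear only in the safety set.

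That interval can be close to zero, or can last about two cycles. At least two of the stated routes out during it, progression and toxicity, may be linked to outcome. The exclusion can therefore select on early outcome. Each cohort is a single arm judged against a fixed historical rate, so no control group shares the selection. Section 11.1 does not say which denominators lie behind the historical rates, so it cannot be checked which analysis set matches them.

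Two things are at stake: an estimate and 90% interval that are too favourable for all who start the combination, and power or type I error that differs from the figures in 11.1.

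**Working it through.** **Inputs.** From 11.1: n = 20 per cohort, with these rules.
- Naive NSCLC and naive RCC: at least 8 responses, null 25%, target 50%.
- Refractory NSCLC and RCC: at least 3, null 5%, target 25%.
- Naive melanoma: at least 11, null 43%, target 68%.
- Refractory melanoma: at least 5, null 15%, target 40%.

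The share *d* of inhibitor starters who are never irradiated is not given. I assume 5% to 20% (1 to 4 of 20). The earlier nelfinavir trial in 1.3 enrolled 16 and treated 12, but that was another regimen and no timing or reasons are given, so I do not use it as an estimate.

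**1. Reproduce the plan.** With X binomial:
- P(X≥8 | 20, 0.25) = 10.2% and P(X≥8 | 20, 0.50) = 86.8%; stated 10% and 87%.
- P(X≥3 | 20, 0.25) = 90.9%; stated 91%.
- P(X≥11 | 20, 0.68) = 92.8%; stated 93%.
- P(X≥5 | 20, 0.40) = 94.9%; stated 95%.

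All agree.

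**2. Length of the gap.** Two cycles of 2, 3 or 4 weeks give at most about 4, 6 or 8 weeks after the first inhibitor dose. The 14.4 calendar shows only 2- to 3-weekly dosing, which differs from the 4-weekly option in 3.1. On the 9.2 schedule the gap closes before the first scan. The calendar key gives a different interval (every 10-12 weeks), and scans may also be done when clinically indicated, so an earlier scan is possible.

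**3. Effect on the estimate.** Worst case: all lost patients are non-responders. Clopper-Pearson 90% intervals:

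| Responses / analysed | Rate | 90% CI |
|---|---|---|
| 5/20 (all starters) | 25.0% | 10.4-45.6% |
| 5/18 (2 lost) | 27.8% | 11.6-49.8% |
| 5/16 (4 lost) | 31.3% | 13.2-54.8% |

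Milder case: lost patients respond at half the irradiated rate. The reported rate is then 0.25/(1 − d/2), so a true 25% becomes 26.3% at d = 10% and 27.8% at d = 20%.

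**4. Operating characteristics, reading A.** 'Evaluable' means inhibitor starters, and the total is held at 120. The analysed n can then be below 20 with the count rules unchanged. If loss is unrelated to response:

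| Cohort (rule) | n=20 | n=18 | n=16 |
|---|---|---|---|
| Naive NSCLC/RCC (≥8) | 86.8% | 76.0% | 59.8% |
| Refractory NSCLC/RCC (≥3) | 90.9% | 86.5% | 80.3% |
| Naive melanoma (≥11) | 92.8% | 81.2% | 59.3% |
| Refractory melanoma (≥5) | 94.9% | 90.6% | 83.3% |

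Type I error does not rise, because dropping patients can only reduce the number of responses counted. If the lost patients are all non-responders, the count is unchanged and type I error for the ≥8 rule stays at 10.2%.

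**5. Operating characteristics, reading B.** 'Evaluable' means the 11.2 set, and accrual continues to 20 irradiated patients. Power at n = 20 is kept. If the rate among all starters is the null 25% and lost patients do not respond, the rate among those analysed is 0.25/(1 − d):
- d = 10%: 27.8%, and P(X≥8 | 20) = 16.5%.
- d = 20%: 31.3%, and P(X≥8 | 20) = 26.7%.

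The stated type I error is 10%.

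**The case against.** The strongest reply is that the restricted set is prespecified and answers the stated question. The objective concerns patients treated with all three components, and 4.1.3 requires measurable disease apart from the irradiated lesion. Counting non-irradiated patients would credit the combination with responses to the inhibitor alone, for which 1.4 quotes rates of about 25-40%. This stands as a reason to keep the three-component set, and as a real cost of changing the primary one. It does not remove the selection when the result is compared with a historical rate.

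Three stronger readings are tempting, and the documents do not support them.

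- **That the analysed n will fall below 20.** Section 6.11 names one non-evaluable group; it does not say that everyone else is evaluable for response. Section 11.1 could mean the 11.2 set with top-up. The 120 maximum does not settle it, because the synopsis does not say whether replaced patients count. The shortfall is one of two readings.
- **That dropping patients turns a failed cohort into a success.** For naive NSCLC/RCC, 8/20 has a 90% interval of 21.7-60.6%, which includes 25%, while 8/16 gives 27.9-72.1%, which does not. But the rule in 11.1 is a count at one-sided 0.10, and the lower limit of a 90% interval is a one-sided 5% bound. Eight responses meet the rule either way, so no declared result changes.
- **That every progressing patient is lost.** Section 6.7 says "this study will allow patients to remain on PD1/PDL1 immune checkpoint inhibitor after apparent radiographic progression", provided benefit-risk is judged favourable. That sits uneasily with 4.3.2, and the two passages need reconciling. Some patients who leave may also have a response recorded under 6.9, although 11.2 plans no response analysis that would use it.

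The frequency is also unknown. A lesion suitable for radiation is an entry requirement, and four non-responders lost out of 20 is an extreme case.

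**Conclusion.** The mismatch between 6.11 and 11.2 is certain on the text; its size is not. Upward bias requires that non-irradiated starters respond less often than irradiated patients. That is plausible given the exit routes in 4.3.2 and 6.8, but no document establishes it. If loss is unrelated to response there is no bias, only lower power under reading A. The worst-case bias and the power losses tabulated for reading A rest on different assumptions and should not be added together.

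Under the assumed 10-20% loss, the overstatement at a true 25% is about 1 to 6 percentage points. For naive NSCLC/RCC the consequence is either power of 76.0% (n=18) or 59.8% (n=16) against 87%, or a false-positive rate of 16.5% or 26.7% against 10%. Which of these applies depends on a definition that the plan does not give. The point should be fixed because the repair is cheap, not because a large error has been shown.

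**What to change.** **In 11.2:** make the primary response set all patients with at least one inhibitor dose, matching 6.11. Code those with no known response as non-responders (2.3.1), including patients never irradiated or never scanned after baseline. Apply the 11.1 counts to the first 20 such patients per cohort. Keep the current three-component set as a prespecified supportive analysis. Report per cohort the number not irradiated, with reasons.

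**In 11.1 and the synopsis:** define 'evaluable for response' in the same way, and state whether the maximum of 120 counts replaced patients. If it does not, the hepatotoxicity boundary in 11.3, which pools all patients and ends at 120, needs extending.

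**Cost.** Wording only; 6.9 already asks for response assessment after discontinuation, subject to the 6.8 exceptions. There are two downsides.

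- The target becomes the response rate among all who start the inhibitor. It may include responses without radiation, and it departs from the objective's 'treated with' wording, which should be aligned.
- If the 50% target holds only in irradiated patients and lost patients never respond, naive NSCLC/RCC power is P(X≥8 | 20, 0.50(1 − d)) = 81.4%, 74.8% or 58.4% at 5%, 10% or 20% loss. The current set gives the same figures under the count rule and the 120 cap, because the same responses are counted. If lost patients respond at half the target rate, the revised set gives 84.3%, 81.4% or 74.8%, against 81.4%, 74.8% or 58.4% for the current one.

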11.0 STATISTICAL CONSIDERATIONS

11.1 Sample Size with Power Justification

The primary objective of this study is to evaluate the response rate in patients with non-small cell lung cancer (NSCLC), melanoma, or renal cell carcinoma (RCC) treated with nelfinavir, radiation therapy and anti-PD-1/PD-L1 therapy. Evaluation of this investigational therapy will be done in disease-specific cohorts separately evaluated by patients naïve to anti-PD-L1/PD-L1 therapy and those with disease refractory to anti-PD-1/PD-L1 therapy.

The total sample size for this study is 20 patients in each of the 6 cohorts (3 disease type by 2 anti-PD-1/PD-L1 exposure groups) for a total of 120 patients evaluable for response. The expected accrual rate is 30 patients per year. The design within each cohort is a single arm, single stage design. The sample size justification for each of the cohorts is follows. Sample size calculations were done using this calculator: <https://stattools.crab.org/Calculators/oneArmBinomial.html>.

Non-Small Cell Lung Cancer (NSCLC):

1. Checkpoint Naïve: In this cohort a true response rate of 50% or greater would be considered evidence of activity whereas a response rate of 25% or less (based on historical data) would not be considered of interest. With 20 patients, this study has 86% power to rule out a response rate of 25%, at the 1-sided 0.10 level if the true response rate were 50%. The observation of at least 8 responses (8/20; 40% ORR) would be

considered evidence to rule out a response rate of 25%. The exact power and type I error for this design are 87% and 10%, respectively.

2. Checkpoint refractory: In this cohort a true response rate of 25% or greater would be considered evidence of activity whereas a response rate of 5% or less (based on historical data) would not be considered of interest. With 20 patients, this study has 91% power to rule out a response rate of 5%, at the 1-sided 0.10 level if the true response rate were 25%. The observation of at least 3 responses (3/20; 15% ORR) would be considered evidence to rule out a response rate of 5%. The exact power and type I error for this design are 91% and 7.6%, respectively.

Melanoma:

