3. Checkpoint Naïve: In this cohort a true response rate of 68% or greater would be considered evidence of activity whereas a response rate of 43% or less (based on historical data) would not be considered of interest. With 20 patients, this study has 84% power to rule out a response rate of 43%, at the 1-sided 0.10 level if the true response rate were 68%. The observation of at least 11 responses (11/20; 55% ORR) would be considered evidence to rule out an rate of 43%. The exact power and type I error for this design are 93% and 19.5%, respectively.
4. Checkpoint refractory: In this cohort a true response rate of 40% or greater would be considered evidence of activity whereas a response rate of 15% or less (based on historical data) would not be considered of interest. With 20 patients, this study has 90% power to rule out a response rate of 15%, at the 1-sided 0.10 level if the true response rate were 40%. The observation of at least 5 responses (5/20; 25% ORR) would be considered evidence to rule out an response rate of 15%. The exact power and type I error for this design are 95% and 17%, respectively.

Renal Cell Carcinoma:

5. Checkpoint Naïve: In this cohort a true response rate of 50% or greater would be considered evidence of activity whereas a response rate of 25% or less (based on historical data) would not be considered of interest. With 20 patients, this study has 86% power to rule out a response rate of 25%, at the 1-sided 0.10 level if the true response rate were 50%. The observation of at least 8 responses (8/20; 40% ORR) would be considered evidence to rule out a response rate of 25%. The exact power and type I error for this design are 87% and 10%, respectively.
6. Checkpoint refractory: In this cohort a true response rate of 25% or greater would be considered evidence of activity whereas a response rate of 5% or less (based on historical data) would not be considered of interest. With 20 patients, this study has 91% power to rule out a response rate of 5%, at the 1-sided 0.10 level if the true response rate were 25%. The observation of at least 3 responses (3/20; 15% ORR) would be considered evidence to rule out a response rate of 5%. The exact power and type I error for this design are 91% and 7.6%, respectively.

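### Section 11.2 states a precision of 18 points at n = 20, which is the normal-approximation value; the 90% Clopper-Pearson interval it names has a half-width of up to 19.8 points

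*Combined protocol and SAP*

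**What the plan says.** Section 11.1 fixes the cohort size: "The total sample size for this study is 20 patients in each of the 6 cohorts". It justifies that number by the power of a one-sided test against a null response rate, not by precision.

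Section 11.2 then covers reporting. Response and toxicity will be "summarized as proportions with associated 90% Clopper-Pearson confidence intervals". The next sentence gives the precision: "With 20 patients per cohort, binary proportions can be estimated to within 18% with 90% confidence". That sentence names no other interval method, is not limited to any range of rates, and is not described as approximate.

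**The concern.** Because the two sentences are adjacent, a reader will take 18% as the precision of the Clopper-Pearson interval. An exact interval at n = 20 is noticeably wider than a normal-approximation interval, so a figure from one method should not be attached to the other.

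What is at stake is only the accuracy of a stated property of the design. For observed rates between 30% and 70%, the published intervals will be wider than the plan says. The naive-cohort thresholds of 8/20 and 11/20 in section 11.1 fall in that range.

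**Working it through.** **Inputs.** n = 20 per cohort (11.1). Two-sided 90% Clopper-Pearson, 5% in each tail (11.2). Stated precision 18 points (11.2). Target and null response rates from 11.1.

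**Step 1: reproduce the plan's figure.** The normal-approximation half-width is largest at a proportion of 0.5:

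1.645 × √(0.5 × 0.5 / 20) = 1.645 × 0.1118 = 0.1839

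This is 18.4 points, which rounds to the stated 18%.

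**Step 2: the named interval.** For x responses out of 20, the lower limit is the 5% quantile of Beta(x, 21 − x) and the upper limit is the 95% quantile of Beta(x + 1, 20 − x). Results are symmetric about x = 10.

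| Count | 90% limits | Half-width (points) | Distance to farther limit (points) |
|---|---|---|---|
| 3/20 | 4.2% to 34.4% | 15.1 | 19.4 |
| 5/20 | 10.4% to 45.6% | 17.6 | 20.6 |
| 6/20 | 14.0% to 50.8% | 18.4 | 20.8 |
| 7/20 | 17.7% to 55.8% | 19.0 | 20.8 |
| 8/20 | 21.7% to 60.6% | 19.5 | 20.6 |
| 9/20 | 25.9% to 65.3% | 19.7 | 20.3 |
| 10/20 | 30.2% to 69.8% | 19.8 | 19.8 |
| 11/20 | 34.7% to 74.1% | 19.7 | 20.3 |

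The half-width is above 18 points for counts 6 to 14 and below it for counts 0 to 5 and 15 to 20. The excess is 0.4 points at counts 6 and 14, and 1.0 to 1.8 points at counts 7 to 13. Measured to the farther limit, the distance is above 18 points for every count from 2 to 18.

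**Step 3: expected half-width by cohort.** Weight each half-width by the Binomial(20, p) probability of its count:

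| True rate p | Cohorts with this target | Expected half-width (points) | Against 18 |
|---|---|---|---|
| 50% | NSCLC naive, RCC naive | 19.4 | +1.4 |
| 40% | Melanoma refractory | 19.0 | +1.0 |
| 68% | Melanoma naive | 18.2 | +0.2 |
| 25% | NSCLC refractory, RCC refractory | 17.1 | −0.9 |

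**Step 4: the other reading.** The sentence could mean that the estimate falls within 18 points of the true rate with 90% probability. At a true rate of 50% that requires 7 to 13 responses, which has probability 88.5%. At 40% it is 89.3%, at 25% it is 93.5%, and at 68% it is 94.9%. Over a fine grid of true rates the minimum is 87.9%, near 48% and 52%. So this reading also falls slightly short of 90% at mid-range rates.

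**Step 5: test the replacement figure.** The maximum Clopper-Pearson half-width is 19.8 points, so 20 covers every count. The probability that the estimate falls within 20 points of the truth is at least 92% at every true rate. The 20-point figure therefore holds on both readings.

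**The case against.** The strongest reply is that the 18% is correct arithmetic for a common planning approximation, and that its sentence names no method. On that view the fault is a missing label, not a wrong calculation. On the probability reading the claim is also nearly right: it reaches 90% over about 78% of all true rates and averages 90.2% over true rates from 30% to 70%.

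The step 3 figures also assume that the target rates are true. At the null rates in 11.1 the expected half-widths are 17.1 points (25%; NSCLC and RCC naive), 10.2 (5%; NSCLC and RCC refractory), 14.5 (15%; melanoma refractory) and 19.2 (43%; melanoma naive). If the regimen adds nothing, the stated precision is therefore met on average in five of the six cohorts. For toxicity at a true rate of 15%, the level used for hepatotoxicity monitoring in 11.3, 18 points is conservative.

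These facts stand, and they keep the point small. They do not remove the mismatch. The claim carries no restriction on the rate, follows directly on a named exact method, and fails for that method across the middle of the range. Rounding turns 18.4 into 18; it does not turn 19.8 into 18. The adjacent 88% chance of observing a toxicity of 10% prevalence is an exact figure (1 − 0.9²⁰ = 87.8%), so a reader has no signal that the 18% is approximate.

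**Conclusion.** The concern holds, as a minor error. The stated 18 points belongs to the normal approximation and understates the half-width of the planned 90% Clopper-Pearson interval for 6 to 14 responses out of 20. The worst case is 1.8 points by half-width, or 2.8 points to the farther limit. If the target rates are true, the expected shortfall is 1.0 to 1.4 points in three cohorts and nil after rounding in a fourth; in the other two the precision is better than stated.

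This rests on 20 evaluable patients per cohort and a two-sided interval with equal tails. Sample size, response thresholds, power and type I error do not depend on the figure.

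**What to change.** In section 11.2, replace the 18% with a half-width of at most about 20 percentage points (farther limit at most about 21) by the 90% Clopper-Pearson method. Labelling the 18% as a normal approximation would also remove the contradiction, but the plan would then quote the precision of an interval it does not intend to report.

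The cost is one clause and a slightly less favourable stated precision. The cohort size, decision thresholds and interval method stay as they are.
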